6.1.1 Acquisition

This study will use only CPAP devices that are clinically approved for the treatment of sleep apnea in Canada, and will be purchased by the study directly from the manufacturer.

6.1.2 Receipt of Device

Upon receipt of the CPAP equipment, an inventory will be performed and a receipt log filled out and signed by the research team member accepting the shipment. Designated study staff will count and verify that the shipment contains all the items noted in the shipment inventory. Any damaged or unusable product in a given shipment will be documented in the study files. We will notify the manufacturer of any damaged or unusable product that was supplied to the site.

6.1.3 Administration of CPAP Intervention

The CPAP intervention will be overseen by one of the study physicians ([name], [name], [name], or [name], with [name] playing principally a consultative role) assisted by a full-time sleep technologist.

To initiate CPAP, participants will come in-person to the study centre to meet with the sleep technologist, who will oversee initial mask fitting and selection, CPAP teaching, and set-up under the direction of the sleep physicians. The technologist will contact participants by telephone or video call according to the study schedule. Calls will address a) anticipation and troubleshooting of common CPAP barriers (mask leak, mask fit, bloating, claustrophobia, etc.) b) education around the OSA physiology and consequences c) motivational enhancement and d) engagement of study partners, following principles shown to be effective at achieving high levels of CPAP adherence in adults with MCI (10). Between scheduled calls, the technologist will be available during business hours as needed for both remote and in-clinic visits.

Participants will be provided an auto-tiltrating CPAP device. CPAP adherence and technical efficacy will be assessed by remotely interrogating participants' CPAP machines. Should high

residual AHI persist, participants may be brought in for an in-lab CPAP titration at the discretion of the study physician.

We will compute several measures of adherence including: 1) % of days adherent, defined as use over 4 hours, for months 0-4 and 5-8, 2) mean nightly usage in hours for months 0-4 and 5-8, and 3) cumulative number of days used >4h since entry into the study (a measure of the total cumulative duration of CPAP adherence). A participant will be considered adherent if they used CPAP for >4h on >80% of nights over the 4-month period.

Risks and side effects related to CPAP are minor and may include: congestion or runny nose, dry mouth, nostrils, eyes, facial pain or skin irritation, claustrophobia. CPAP is not an experimental device and is being used in this study according to its intended use. In the unlikely event of an emergency related to CPAP use, participants will receive the same care as they would in usual care pathways. That is, participants are encouraged to contact the sleep technologist for the study during business hours. If the emergency is more urgent, participants are encouraged to use local emergency services, and then contact the sleep technologist for the study during business hours.

6.2 Brain Health PRO platform (BHP)

The BHP web-based education platform (11) is a 45-week, multidomain, web-based formal educational program designed to increase dementia literacy, foster engagement, and convey best available evidence for lifestyle changes that can mitigate dementia risk. The program was developed as a collaborative effort by CCNA investigators with recognized expertise in the program's content areas, along with input from older-adult citizen advisors. The program was refined and updated based on feedback from focus-groups and a 3-month pilot study to assess usability and accessibility.

This protocol will utilize the sleep modules of the BHP platform covering sleep physiology, healthy sleep habits, and information about sleep disorders like sleep apnea.

6.2.1 Administration of BHP Intervention

Participants in both groups will register at baseline on the BHP website and obtain a personal password. Participants will need to provide a valid e-mail address and password in order to login and participate in BHP. Participants will also be asked to enter a preferred name (this can be a first name or nickname), which they will be referred to as throughout their participation in the program. Name and e-mail address will not be included in the study data set. All data from BHP will be de-identified and linked to participant study ID prior to being included in our dataset. Registration will also include viewing a brief video explaining the program.

The program content consists of 24 chapters discussing the following topics. Participants will be invited to read the content at their own pace and will be given the opportunity to discuss with research staff at scheduled check-in calls. Specific chapters are:

- 1) What is sleep?
- 2) How do we sleep?

- 3) Measuring sleep
- 4) Why do we sleep – Emotional health and well-being
- 5) Why do we sleep – Physical health
- 6) Why do we sleep – To strengthen memory
- 7) How much sleep do you need?
- 8) Dreams
- 9) Sleep changes across adulthood and factors that may disturb sleep
- 10) Insomnia
- 11) Insomnia 2
- 12) Daytime sleepiness
- 13) Sleep apnea: Definition, symptoms, causes
- 14) Sleep apnea: Treatments
- 15) Restless legs syndrome
- 16) Movements during sleep
- 17) REM sleep behavior disorder (RBD)
- 18) Disrupted sleep: when to be concerned
- 19) Sleep in Alzheimer's disease
- 20) Sleep in Parkinson's Disease
- 21) Lighting up the aging brain: the effects of light
- 22) Sleep and physical activity
- 23) Recommendations for better sleep
- 24) Sleep and sex differences

We will track adherence through metadata from the BHP platform that can be exported by the study team and includes: participant ID, date an account was created, and date specific chapters are read.

7 STUDY SCHEDULE AND PROCEDURES

7.1 Overview of Study Schedule

An overview of the study schedule can be found in Appendix B.

7.2 Study Instruments

Copies of each study instrument can found in Appendix D.

7.2.1 *Eligibility Screening and Basic Information*

Screening Checklist for Eligibility: The screening checklist for eligibility is a simple document with inclusion and exclusion criteria. All inclusion criteria and no exclusion criteria must be met to be eligible (video conference). See Appendix C-1.

Demographic and Medical Information: Basic demographic and medical information include age, sex, education, and past/present medications and medical comorbidities. (video conference). See Appendix C-2.

7.2.2 *Sleep Disorders and Patient Reported Sleep Outcomes*

Sleep Apnea: As an initial screen for sleep apnea, we will use the STOP-Bang questionnaire completed on an online form (12). See Appendix C-3.

Insomnia Severity Index (ISI): A 7-item questionnaire assessing sleep onset, sleep maintenance, sleep satisfaction, and sleep problems. Each item is rated on a scale ranging from 0-4 with total scores ranging from 0 to 28 and higher scores suggesting more severe insomnia (13). The ISI is administered as a questionnaire which can be administered via any interphase (face-to-face or video conferencing). We will administer it via video conferencing. See Appendix C-4.

Restless Legs. RLS will be assessed using the 8-item Cambridge Hopkins Questionnaire (14) administered by video conference. See Appendix C-5.

REM Sleep Behaviour Disorder RBD will be assessed using a single question from the Mayo sleep questionnaire: “Have you ever been told, or suspected yourself, that you seem to ‘act out your dreams’ while asleep (for example, punching, flailing your arms in the air, making running movements, etc.)?” (15). See Appendix C-6.

Self-Report Sleep Quality: We will use the PROMIS Sleep Disturbance and PROMIS Sleep Related Impairment short form questionnaires to assess subjective sleep quality (16). See Appendix C-7.

Sleep Diary: We will use a 10-day sleep diary to complement the accelerometry data. See Appendix C-8.

7.2.3 *Cognitive Evaluation*

Montreal Cognitive Assessment: The Full MoCA via Audio-Visual Conference consists of a 30-point test assessing the following items: short term memory recall, visuospatial abilities,

executive functioning, phonemic fluency, verbal abstraction, attention, concentration, working memory, language, and orientation (17). The remote version of the MoCA will be administered using the validated online full MoCA (version 8.1) via audio-visual conference (18). See Appendix C-9.

Logical Memory: Logical Memory I & II (Story A) from the Wechsler memory scale assesses memory and free recall (19). This test will be completed via video conferencing in which the participant will be instructed to listen to a story and repeat it back after it has been read to the best of his/her ability. The participant will then be asked to recall the story approximately 30 minutes later. Because this test is an auditory test to begin with (i.e., it does not require visual stimuli such as paper and pencil questionnaires), it can be administered using any modality (face-to-face or via video conference). We will conduct it via video conferencing. See Appendix C-10.

Geriatric Depression Scale: The GDS Short Form is a brief, 15-item questionnaire in which participants are asked to respond by answering yes or no in reference to how they felt over the past week (20). See Appendix C-11.

Symbol Digit Modalities Test (SDMT): Our primary outcome measure is the total score on the SDMT, a test of speeded executive function. A recent study estimated a minimal clinically important difference in the SDMT in a sample of adults with MCI of -3.8 points, corresponding to an effect size of -0.42 (2). An observational study of CPAP in adults with MCI found a similar effect size of CPAP (6-month effect size 0.46) on a very similar test, the Digit Symbol Substitution Test subtest of the Wechsler Adult Intelligence Scale (3). The test-retest correlation for the SDMT in clinically stable individuals with MCI over a mean follow-up of 19 months is 0.78 (2). See Appendix C-12.

Trail Making Test A&B: The TMT A & B is a two-part test that assesses attention speed, and mental flexibility and has been widely used in clinical settings for assessing deficits in attention and executive functioning (21). See Appendix C-13.

Digit Span: The digit span forward and backward from the WAIS-III will be administered as an assessment of working memory (21). See Appendix C-14.

Letter Number Sequencing: The Letter Number Sequencing Test (23) is a test of working memory.

The Hopkins Verbal Learning Test-Revised (HVLT-R): A brief, multicomponent word-list learning task that was developed by Brandt and Benedict (24) to assess verbal learning and memory. The HVLT-R consists of three free recall learning trials, a delayed recall trial and a recognition task, and yields a number of raw and calculated scores including total recall score, delayed recall score, percentage retention and a recognition discrimination index (RDI). See Appendix C-15.

ADAS-Cog: The ADAS-Cog-13 consists of 13 brief cognitive tests assessing memory, language, attention, concentration, and praxis. Scores range from 0 to 85 with higher scores indicating increased severity of cognitive impairment. See Appendix C-16.

7.2.4 Functional Status

IADL: The Lawton-Brody Instrumental Activities of Daily Living (IADL) scale measures participant's ability to engage in instrumental activities of daily living via questionnaire assessing activities such as preparing meals and managing personal finances (25). Responses range from

0 (normal ability) to 3 (dependent for functioning) with total scores ranging from 0 to 23. This assessment of functional independence is collected via questionnaire, which can be administered via any interface (face-to-face or video conferencing). We will administer it via video conferencing. See Appendix C-17.

7.2.5 Sleep Physiology

Sleep Apnea: At screening baseline, 16 weeks, and 32 weeks, participants will undergo 1 night of Apnealink from which we will extract oximetry metrics including ODI, AHI, mean SpO₂, hypoxia burden, and time with SpO₂<92%. An entry requirement will be ODI \geq 5 OR time with SpO₂<92% of >10 minutes. The ApneaLink is an FDA-approved self-administered 3-channel portable device that assesses for sleep apnea based on airflow as assessed using an intra-nasal pressure transducer, pulse oximetry assessed using a finger probe, and respiratory effort using a band around the chest. It is considered a Type 4 sleep monitor by the American Academy of Sleep Medicine and has been validated against polysomnography (26).

EEG: At baseline, 16 weeks and 32 weeks, participants will undergo 3 nights of home EEG using a wearable headband (MUSE-S, Interaxon, Toronto) which will undergo automated sleep staging using a random forest based model developed by our lab based on 308 MUSE-S recordings with simultaneous in-lab PSG. To develop our own model, we divided our set of n=308 recordings with simultaneous PSG-MUSE EEG recordings randomly into n=215 training and n=93 test recordings. The MUSE-S provides four-channel EEG, triaxial accelerometer (ACC), and PPG data. After segmentation into 30-second epochs and normalization of each channel within each epoch, we extract statistical and morphological features are extracted from each epoch. EEG signals undergo bandpass filtering to isolate frequency components, enabling the extraction of power spectral density (PSD) across different frequency bands (Delta, Theta, Alpha, Beta, Gamma). Similarly, PPG data is filtered and denoised before features such as PSD, dominant frequency, heart rate variability, and respiratory rate are extracted. For sleep stage classification, a 1-D Convolutional Neural Network (CNN) architecture is employed. Ground truth labels were obtained from visual analysis of simultaneously recorded full PSG. Extracted features from MUSE EEG, accelerometer, and PPG data are fed into the model, which consists of Conv1D layers with ReLU activation, followed by MaxPooling1D layers. The hierarchical features extracted by the CNN are then flattened and passed through densely connected layers with ReLU activation. The output layer employs softmax activation to output class probabilities. The model is trained using categorical cross-entropy loss and the Adam optimizer, with a learning rate of 0.001, over 10 epochs with a batch size of 32. For sleep vs wake classification, a Decision Tree classifier is used. This classifier is configured with specific parameters controlling its complexity and generalization ability, such as with a Gini impurity criterion for splitting, limiting the maximum depth of the tree to 50, and setting minimum samples per leaf to 5 and minimum samples for splitting to 5. Post-processing involves applying majority voting on predicted sleep stages to smooth transitions and enhance the coherence of the sleep architecture. Finally, the performance of the trained models, whether binary or multiclass, is evaluated using appropriate metrics such as accuracy, sensitivity, specificity, and F1-score. Sleep metrics such as total recording time, total sleep time, sleep latency, and time spent in different sleep stages (N1, N2, N3, and REM) are calculated over all test subjects to assess the efficacy of the classification pipeline. . In the n=93 test set, we saw improved performance compared to the manufacturer provided model, correctly classifying a much larger proportion of epochs of slow wave sleep (72% vs. 56%), REM sleep (89% vs. 71%), and wake (94% vs. 71%).

Accelerometry The AX3 is an accelerometer used to detect movement, vibrations, and orientation changes. The AX3 will be mailed to participants and a sponsor site study team member will instruct the participant on the proper application and use of the device through videoconference. The participant will be given a copy of the instruction script, in addition to an instruction card containing contact information of research staff should they have any questions. The participant will be shown how to place the device on their non-dominant wrist by research staff, and participants will be instructed to wear the device continuously for 10 days, even when bathing or swimming. During the 10 days, participants will be asked to track their work and sleep hours in a diary. At the end of 10 days, participants will return the device to the sponsor site using a pre-paid parcel system. This procedure will be repeated at 4 months and 8 months

7.2.6 CPAP Adherence

CPAP adherence will be automatically logged by the CPAP devices for the duration of the study period, and accessible remotely from the study centre. We will compute several measures of adherence including: 1) % of days adherent, defined as use over 4 hours, for months 0-4 and 5-8. 2) mean nightly usage in hours for months 0-4 and 5-8 3) cumulative number of days used >4h since entry into the study (a measure of the total cumulative duration of CPAP adherence).

7.2.7 MRI Brain

Participants will be imaged using the Canadian Dementia Imaging protocol consisting of a 3D T1, interleaved 3mm PD/T2, 3D FLAIR, T2*, DTI, and resting state BOLD. Perivascular spaces and white matter hyperintensities will be quantified with the SynthSegCSVD algorithm developed and validated in our laboratory, a robust neural network based (i.e. applies an AI deep learning method) tool. The SegCSVD_{PVS} segmentation model employs a convolutional neural net (CNN) based on the UNet architecture and incorporates several advanced machine learning techniques to ensure accurate and robust PVS segmentation. Central to the development of SegCSVD_{PVS} was the curation of a diverse dataset consisting of T1-weighted images sourced from several multi-site studies spanning a wide range of patient populations. Ground truth PVS labels for this dataset were generated using a semi-automated procedure consisting of: “RORPO” filtering to identify small tubular structures on the T1; false positive minimization using the FreeSurfer segmentation output; and manual refinement by a trained image analyst to correct any remaining errors.

7.2.8 Plasma Samples

Collection: Blood samples (10 ml) will be collected in plasma vacutainer tubes and centrifuged at 1000×g for 10 minutes. Plasma will be separated and preserved in a freezer at -80°C in a secure freezer. All samples will be de-identified and preserved at -80°C and assayed together in a batch after the collection of the last sample

Vascular Risk Factors: Classical vascular risk factors will also be assessed (lipid profile including LDL, HDL, and triglycerides; fasting glucose; haemoglobin A1C)

Plasma AD Biomarkers: We will assess plasma pTau181 (for AD pathology) and GFAP (for astrocyte activation). pTau181 has been shown to be strongly predictive of both amyloid and tau pathology as measured by PET (4,5) while plasma GFAP correlates strongly with ¹⁸F-SMBT-1 PET, a marker of brain reactive astrocytes (6).

7.3 Premature Withdrawal

Participants may be withdrawn or be discontinued from the study for any of the following reasons:

1. At the participant's request (withdrawal of consent)
2. At the discretion of the investigator, if deemed appropriate, for any reason
3. If an intolerable or life-threatening adverse event occurs

Participant data collected to the date of discontinuation or withdrawal will be included in the analysis.

7.4 Study Close-Out

At the close of the study, participants will be able to keep their CPAP equipment. Clinical care will initially continue with the study physician, but arrangements will be made to transfer clinical care to another physician if desired by the study participant. Ongoing CPAP support would be transitioned to local CPAP suppliers.

7.5 Protocol Deviations

It is the responsibility of the investigator to ensure that only investigative procedures, as outlined in this protocol are performed on study participants; the occurrence of deviations from the protocol or SOPs are limited; and compliance with the regulations is maintained. Planned deviations from the protocol must not be implemented without prior agreement from the sponsor and approval from the local REB, as required, unless to eliminate an immediate hazard to a participant.

Planned or unplanned deviations may occur on the part of the participant, the investigator, or study research team. In resolution to a deviation, corrective/preventative actions are to be developed and implemented in a timely manner. Protocol deviations will be documented and reported as required and assessed where necessary during analysis.

8 ASSESSMENT OF SAFETY

The safety of research participants is foremost and should always be considered throughout the conduct of research.

8.1 Definitions

8.1.1 *Adverse Events*

An adverse event (AE) is any untoward medical occurrence in a participant that occurs from the time of enrollment and up to 30 days after study participation has ended. For the purposes of reporting, an AE is defined as any unfavourable or unintended sign (e.g., including an abnormal laboratory finding), symptom, or disease associated with study procedures that are both non-serious and either temporally or causally related to study procedures. Pre-existing conditions, which increase in frequency or severity or worsen in nature during, or as a consequence of, a study procedure, may also be considered an AE if it meets the definition of being both non-serious and related to a study procedure.

An AE does not include:

- Medical or surgical procedures (e.g., surgery, endoscopy, tooth extraction, transfusion).
- The condition that leads to the procedure is the AE.
- Situations where an untoward medical occurrence has not occurred (e.g., hospitalization for elective surgery, social and/or convenience admissions).
- Worsening of symptoms associated with expected decline in memory or an associated co-morbid condition and not related to a study procedure.
- Those medical or surgical adverse events that are not related to the study procedures

8.1.2 *Serious Adverse Events*

A serious adverse event (SAE) or reaction is any untoward occurrence related to study procedures that:

- Results in death,
- Is life-threatening,
- Requires inpatient hospitalization or prolongation of existing hospitalization,
- Results in persistent or in significant disability/incapacity,
- Is a congenital abnormality or a birth defect.

The term "life-threatening" in the definition of "serious" refers to an event in which the participant was at risk of death at the time of the event; it does not refer to an event which hypothetically might have caused death if it were more severe.

8.1.3 *Unexpected Adverse Event*

An unexpected adverse event is any AE that is not identified in nature, severity or frequency in the relevant safety document(s) or is not identified as a possible risk in the study protocol or the

informed consent form.

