8.3 Adverse Event Recording

All AEs both non-serious and either temporally or causally related to study procedures (i.e., a new event or an exacerbation of a pre-existing condition) that occur from the time of enrollment and up to 30 days after study participation has ended will be recorded as an AE. The Investigator must follow all AEs until the AE resolves, or until the Investigator determines the event is chronic or clinically stable. If an AE remains unresolved at the conclusion of the AE reporting period, the Investigator will make a clinical assessment to determine whether continued follow-up of the AE is warranted. The Investigator should attempt to establish a diagnosis of the event based on signs, symptoms and/or other clinical information. In such cases, the diagnosis should be documented as the AE and not the individual signs/symptoms.

The following are not considered AEs and therefore do not require recording:

- Pre-existing diseases or conditions identified and recorded at screening/baseline unless, at the discretion of the investigator, the disease or condition worsens in severity or frequency
- At the discretion of the investigator, events considered likely manifestations of the underlying disease or that commonly occur in the study population independent of study procedures
- Elective medical or surgical procedures.

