8.4.2 Investigator reporting: Notifying the Sponsor

The investigator is responsible for reporting serious adverse events and unanticipated events to the sponsor in accordance with applicable regulations and reporting requirements and timelines.

Events that are assessed to be **serious and unexpected and related or cannot be ruled out as related** to the study procedures are reportable. Reporting should include a description of the event in sufficient detail to allow for a complete medical assessment of the case and independent determination of possible causality. The minimum information required includes at least one identifiable participant, one identifiable reporter, one serious reaction, and one suspect procedure.

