8.5 Reporting and Entry Timelines

Study investigators will report SAEs to the sponsor within the following timelines:

- All deaths and immediately life-threatening events, whether related or unrelated, will be recorded and reported to the sponsor within 24 hours of site awareness.
- Serious adverse events other than death and immediately life-threatening events, regardless of relationship, will be reported to the sponsor within 72 hours of site awareness.

Adverse event information will be entered into the CRF in a timely manner and **no later than 15 days** from the time the investigator becomes aware of the event.

Serious adverse event information will be entered into the CRF in a timely manner and **within 72 hours** from the time the investigator becomes aware of the event.

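### Relatedness is built into the SAE definition (8.1.2) although 8.5 requires SAEs whatever their cause, so some events, chiefly those attributed to untreated OSA, can go unrecorded and capture may differ by arm

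*Protocol*

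**What the plan says.** Five parts of protocol section 8 decide which events are recorded or reported.

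- **8.1.1 (AE).** It opens broadly: "An adverse event (AE) is any untoward medical occurrence in a participant", within a window from enrolment to 30 days after participation. For reporting it then narrows an AE to events that are "both non-serious and either temporally or causally related to study procedures". Its list of things that are not AEs ends with "Those medical or surgical adverse events that are not related to the study procedures".
- **8.1.2 (SAE).** An SAE "is any untoward occurrence related to study procedures that" leads to death, threat to life, hospitalisation, disability or a birth defect.
- **8.3 (recording).** The investigator may, at discretion, leave out "events considered likely manifestations of the underlying disease or that commonly occur in the study population independent of study procedures".
- **8.4.2 (notifying the sponsor).** The first paragraph makes the investigator responsible for reporting SAEs and unanticipated events. The second says that the reportable events are those assessed as "serious and unexpected and related or cannot be ruled out as related".
- **8.5 (timelines).** "All deaths and immediately life-threatening events, whether related or unrelated, will be recorded and reported to the sponsor within 24 hours of site awareness". Other SAEs, "regardless of relationship, will be reported to the sponsor within 72 hours".

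Section 8.2.1 adds a default: if the investigator is unsure about causality, the event is handled as related for reporting purposes.

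**The concern.** If relatedness is part of the definition of an SAE, the instruction in 8.5 to report SAEs whatever their cause has nothing to act on for an unrelated event. A site faced with, say, a hospitalisation that it considers unrelated cannot tell from the protocol whether an SAE form is due.

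The design makes this more than a drafting slip. Under 4.1 the Later CPAP group has no CPAP for the first 4 months, although everyone enrolled has moderate-severe OSA. Harm from that delay would come from the untreated disease and not from a study procedure. The protocol recognises this kind of harm: 5.2 excludes people with recent drowsiness-related driving accidents or near misses, 12.3 presents that exclusion as an ethical safeguard, and the supporting letter mentions accidents from impaired attention, though at a low rate. A filter on procedure-relatedness can remove such events while keeping those that CPAP causes. Data never collected cannot be recovered by any later analysis plan.

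**Working it through.** No arithmetic applies: the protocol states no safety event rate and no safety sample size. The check takes typical events in months 0-4 through each rule.

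| Event | 8.1.1 / 8.3 | 8.1.2 | 8.4.2, second paragraph | 8.5 | Result |
|---|---|---|---|---|---|
| Death or immediately life-threatening event, judged unrelated | Not an AE (serious, unrelated) | Not an SAE | Not reportable | Must be recorded and reported in 24 hours | Covered by 8.5 |
| Hospitalisation or disability, not life-threatening, attributed to untreated OSA | Not an AE (serious, unrelated) | Not an SAE | Not reportable | Due in 72 hours if seriousness is judged by outcome; not reached if the 8.1.2 definition applies | Contradictory; can be left out |
| Non-serious accident or fall attributed to untreated OSA | Inside the opening sentence; outside under the last exclusion; omission allowed by 8.3 | Not applicable | Not applicable | Only a 15-day entry timeline for AEs; does not restore it | Can be left out |
| Event with uncertain cause | Handled as related (8.2.1) | Handled as related | Reportable if serious and unexpected | Covered if serious | Covered |
| Event caused by CPAP | AE if non-serious | SAE if serious | Reportable if serious and unexpected | Covered if serious | Covered |
| Event caused by phlebotomy, MRI or another shared procedure | AE if non-serious | SAE if serious | Reportable if serious and unexpected | Covered if serious | Covered |

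Four things follow.

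1. **For SAEs the conflict is between sections.** 8.1.2 makes relatedness a condition; 8.5 says it does not matter. 8.4.2 stays narrower than 8.5 unless it is meant only as an expedited-reporting rule, which it does not say.
2. **For non-serious AEs the conflict is inside 8.1.1,** between its opening sentence and its exclusions. 8.5 is not the opposing text here, because its wording on relationship covers only deaths, life-threatening events and SAEs.
3. **One class falls between the definitions.** An unrelated serious event is not an AE for reporting, because it is serious, and not an SAE, because it is unrelated.
4. **The arms differ in one relevant procedure.** In months 0-4 CPAP is a study procedure for the Early group only. CPAP-related events (fifth row) can arise only there. Harm from going without CPAP (second and third rows) is the particular risk of the Later group. A relatedness condition therefore need not act equally on the two arms.

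**The case against.** The strongest reply is that 8.5 is the working rule and is broad enough. Its sentence on deaths and immediately life-threatening events does not use the term SAE, so it holds whatever 8.1.2 says. Its second rule makes sense only if seriousness is judged by outcome, which is how 8.2.4 describes it. The reporting definition in 8.1.1 and the recording rule in 8.3 also accept a temporal relation, 8.2.1 resolves doubt towards related, and the first paragraph of 8.4.2 is general.

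Most of this stands, and it narrows the gap. The gravest events are covered. What remains is the event with a confident attribution to the disease: 8.2.1 does not apply, the last exclusion in 8.1.1 works against the temporal wording, and 8.2.3 refers seriousness back to 8.1.2, which restores the condition.

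A reader might infer more than the text supports:

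- **That attribution is made unblinded.** 8.2.1 assigns causality to the investigator or a delegate and does not state whether they are blinded.
- **That the first stopping rule in 9.3 is compromised.** That rule concerns adverse events of the intervention, which the relatedness-based definitions do capture. It is not written as a rule on harm from delayed CPAP.
- **That a planned safety comparison is biased.** 9.4 describes no between-arm safety analysis; one may exist in a SAP not shown.
- **That a loss can be quantified.** No event rate is given, and an illustration with equal unrelated rates in both arms would show equal loss, not asymmetry.
- **That the control arm has nothing to which an event could be related.** The Later group receives BHP-sleep, phlebotomy, MRI and wearables.

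**Conclusion.** The point holds in a limited form. 8.1.2 and 8.5 cannot both be followed for an unrelated SAE, 8.4.2 adds a third standard, and 8.1.1 contradicts itself on unrelated AEs. As written, two classes can be left out: serious events that are not life-threatening, and non-serious events, when either is confidently attributed to untreated OSA. Capture may differ by arm in months 0-4.

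The size cannot be stated from the protocol. The conclusion assumes only that some such events occur and that some sites apply the definitions literally. The contradiction is certain; the difference between arms is a possibility, not a demonstrated bias. The wording should be changed because event collection is fixed in the protocol.

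**What to change.** This is wrong as written and needs a wording amendment:

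- In 8.1.2, remove the relatedness condition, so that an SAE is defined by its outcome.
- Reconcile 8.4.2 with 8.5. If 8.4.2 is meant as a narrower rule for expedited or onward reporting, say so.
- Reconcile the opening of 8.1.1 with its reporting definition and exclusion list, and reconcile the discretionary exemption in 8.3 with both, so that events are recorded by the same rule in both arms from enrolment.
- Keep relatedness as a recorded attribute of each event, assessed under 8.2.1, and not as a condition for recording it.

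The cost is some additional event forms in a trial of an approved device whose stated risks are minor. Treatment and the visit schedule do not change.
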